7.9.1.3.10 Lost days from school or work

Summary number of lost days from school or work will be reported during study phase and continuation phase.

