9.3. STUDY PHASE

Treatment Arm	Control Arm

Visit 5A: Pump Start [Visit 4 + 7 days (Window \pm 7 day)]
 
Note: Visit 4 and Visit 5A can be combined to start pump therapy.
 
This visit can be done remotely or onsite.
 
Site staff will:
 
▪ Train subject on the AHCL insulin pump and subject starts using the insulin pump at this visit.▪ Set-up subject CareLink Account.▪ Train subject to perform weekly CareLink uploads.▪ Dispense/Ship supplies to subject (indicative quantity for 1 month):
 1 AHCL insulin pump 250 Strips 10 Infusion sets (1 box of 10) 10 Reservoirs (1 box of 10) 8 AA batteries (2 packs of 4)	
Visit 5: Follow-up call [Visit 4 + 7 days (Window \pm 5 days)]
 
Study staff will call the subject to:
 
▪ Review therapy / Adjust settings.▪ Review adverse event or device deficiency, if any.

Treatment Arm	Control Arm

▪ Review adverse event or device deficiency, if any. 
If Visit 6A is planned to be conducted remotely: Site staff can start CGM training at Visit 5A and dispense/ship supplies to subject (indicative quantity for 3 months):
 
○ 1 Guardian Link 3 Transmitter kit○ 20 sensors○ 750 strips○ 30 Infusion sets (3 boxes of 10)○ 30 Reservoirs (3 boxes of 10)○ 12 AA batteries (3 packs of 4) 
Visit 5B: Pump Training Follow-Up [Visit 5A + 3 days (Window \pm 1 day)]
 
This visit can be done by phone or onsite.
 
Site staff will:
 
▪ Subject will be trained on first infusion set change and receive additional retraining on pump, as needed.▪ Review AHCL therapy / Adjust settings.▪ Review adverse event or device deficiency, if any. 
If the visit is conducted onsite, site staff will additionally:
 
▪ Upload the AHCL into CareLink. Use correct Subject ID (327-XXX-XXX).	

Treatment Arm	Control Arm

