
Visit 7A [Visit 5A + 3 months (Window ± 10 days)] This visit can be done remotely or onsite.
 
Site staff will:
 
▪ Collect blood sample for HbA1c (central lab kit). If visit is conducted remotely, a nurse visit can be organized with the subject to collect the blood sample.▪ Upload AHCL into CareLink, if visit is onsite. Use correct Subject ID (327-XXX-XXX).▪ Ensure CareLink upload was done / Advise subject to perform weekly CareLink uploads▪ Review AHCL therapy / Adjust settings▪ Retrain subject on Pump/CGM as needed▪ Review adverse event or device deficiency, if any.▪ Dispense/Ship supplies to subject (indicative quantities for 3 months):
○ 750 Strips○ 20 sensors○ 30 Infusion sets (3 boxes of 10)○ 30 Reservoirs (3 boxes of 10)○ 12 AA batteries (3 packs of 4)	
Visit 7A [Visit 5 + 3 months (Window ± 10 days)] This visit can be done remotely or onsite.
 
Site staff will:
 
▪ If the visit is planned remotely, site staff will ship the following supplies to the patient prior to the visit:
○ Blinded CGM Diary○ 1 Contour Next Link 2.4 (subject uses same meter as dispensed previously)○ 80 Strips○ 2 Transmitters (1 is back-up)○ 4 sensors (2 are back-up)○ Charger○ One-press Serter▪ Collect blood sample for HbA1c (central lab kit). If visit is conducted remotely, a nurse visit can be organized with the subject to collect the blood sample.▪ Review therapy / Adjust settings▪ Review adverse event or device deficiency, if any▪ Record % of use of CGM and average number of scans and % of sensor readings for FGM over the previous month (based on downloaded and printed report). If the

Treatment Arm	Control Arm

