
Visit 8: Follow-Up Visit [Visit 7A + 3 months (Window \pm 10 days)]
 
This visit can be done remotely or onsite.
 
▪ Ask subject to complete questionnaires HFS, DTSQs, DTSQc and DQoL during the visit. If the visit is planned remotely, site staff will send the questionnaires HFS, DTSQs, DTSQc and DQoL to the subject prior to the visit and subject will send them back to site upon completion.▪ Collect blood sample for HbA1c (central lab kit). If visit is conducted remotely, a nurse visit can be organized with the subject to collect the blood sample.▪ Upload AHCL into CareLink, if visit is onsite. Use correct Subject ID (327-XXX-XXX).▪ Ensure CareLink upload was done / Advise subject to perform weekly CareLink uploads▪ Review AHCL therapy / Adjust settings▪ Retrain subject on Pump/CGM as needed▪ Review adverse event or device deficiency, if any▪ Measure/Collect height and weight.▪ Dispense/Ship supplies to subject (indicative quantity for 3 months):
○ 20 sensors○ 750 Strips○ 30 Infusion sets (3 boxes of 10)○ 30 Reservoirs (3 boxes of 10)○ 12 AA batteries (3 packs of 4)	
Visit 8: Follow-Up Visit [Visit 7A + 3 months (Window \pm 10 days)]
 
This visit can be done remotely or onsite.
 
If the visit is planned remotely, site staff will send the following supplies/documents to the subject prior to the visit:
 
○ Blinded CGM Diary○ 1 CONTOUR NEXT LINK 2.4 (subject uses same meter as dispensed previously)○ 80 Strips○ 2 Transmitters (1 is back-up)○ 4 sensors (2 are back-up)○ Charger○ One-press Serter○ Questionnaires HFS, DTSQs, DTSQc and DQoL 
▪ Ask subject to complete questionnaires HFS, DTSQs, DTSQc and DQoL during the visit and to send them back upon completion▪ Collect blood sample for HbA1c (central lab kit). If visit is conducted remotely a nurse visit can be organized with the subject to collect the blood sample.▪ Review therapy / Adjust settings▪ Review adverse event or device deficiency, if any.▪ Measure/Collect height and weight▪ Record % of use of CGM and average number of scans and % sensor readings for FGM over the previous month (based on downloaded report). If the visit is conducted remotely, the site can call the subject and record the data in medical chart or the subject can share the report via email.▪ (Re)Train the subject on Blinded CGM usage (sensor insertion, transmitter use).

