
Treatment Arm	Control Arm
	
▪ Advise subject to perform at least 4 fingerstick blood glucose measurements per day with the study meter.▪ Provide Blinded CGM Diary to Subject▪ Dispense supplies to subject (indicative quantity for 3 weeks):
○ 1 CONTOUR NEXT LINK 2.4 (subject uses same meter as dispensed previously)○ 80 Strips○ 2 Guardian Link 3 Transmitters (1 is back-up)○ 4 sensors (2 are back-up)○ Charger○ One-press serter

Treatment Arm	Control Arm

Visit 9: End of Study Phase [Visit 8 + 14 days (Window + 7 days)]
 
Site staff will call the subject to:
 
▪ Ensure CareLink upload was done / Advise subject to perform weekly CareLink uploads▪ Review AHCL therapy / Adjust settings▪ Review adverse event or device deficiency, if any.▪ Plan the next visits until Visit 13.	
Visit 9: End of Study Phase / Pump Start [Visit 8 + 14 days (Window + 7 days)]
 
This visit can be done remotely or onsite.
 
If the Visit 9 is conducted remotely, the subject will return the devices dispensed at Visit 8 via post-mail/courier, using the provided shipping box. Upon receipt of the supplies at the site, site staff will conduct Visit 9.
 
▪ Collect/Receive from the subject:
○ 1 Blinded CGM Diary○ 2 Guardian Link 3 Transmitters○ 1 CONTOUR NEXT LINK 2.4 meter○ 1 Charger○ One-press serter○ Unused Sensors▪ Upload data from the Meter in CareLink using correct Subject ID (327-XXX-XXX).▪ Upload data of Transmitter using the Download utility. Make sure to use correct file name (Subject ID_Visit9_DATE). Refer to Blinded CGM Instructions for more details.▪ Record % of use of CGM and average number of scans and % sensor readings for FGM over the previous 2 weeks (based on downloaded and printed report). If the visit is conducted remotely, the site can call the subject and document this in medical chart or subject can share the report via email.▪ Review adverse event or device deficiency, if any.▪ Site staff will train subject on the AHCL insulin pump and subject starts using the insulin pump.▪ Set-up subject CareLink Account.▪ Train subject to perform weekly CareLink uploads.

Treatment Arm	Control Arm

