
Visit 12 [Visit 11 + 1 month (Window ± 10 days)] This visit can be done remotely or onsite.
 
▪ Upload AHCL into CareLink if visit is onsite. Use correct Subject ID (327-XXX-XXX).▪ Ensure CareLink upload was done / Advise subject to perform weekly CareLink uploads.▪ Review AHCL therapy / Adjust settings.▪ Retrain subject on Pump/CGM as needed.▪ Review adverse event or device deficiency, if any.▪ Plan next visit with subject in 3 months.▪ Dispense/ship supplies to subject (indicative quantity for 3 month):
○ 20 sensors○ 750 Strips○ 30 Infusion sets (3 boxes of 10)○ 30 Reservoirs (3 boxes of 10)○ 12 AA batteries (3 packs of 4)	
Visit 12 [Visit 11E + 1 month (Window ± 10 days)] This visit can be done remotely or onsite.
 
▪ Upload AHCL into CareLink if visit is onsite. Use correct Subject ID (327-XXX-XXX).▪ Ensure CareLink upload was done / Advise subject to perform weekly CareLink uploads.▪ Review AHCL therapy / Adjust settings.▪ Retrain subject on Pump/CGM as needed.▪ Review adverse event or device deficiency, if any.▪ Plan next visit with subject in 3 months.▪ Dispense/ship supplies to subject (indicative quantity for 3 months):
○ 20 sensors○ 750 Strips○ 30 Infusion sets (3 boxes of 10)○ 30 Reservoirs (3 boxes of 10)○ 12 AA batteries (3 packs of 4)

Treatment Arm	Control Arm

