5.1 Duration

Overall study duration from first subject enrollment until the last subject exit is expected to last approximatively 25 months, including an estimated 6-month site activation period, 6-month enrollment period, and a 13-month follow-up period for each subject.

Each subject will enter a run-in phase of approximately 2 weeks, followed by a study phase of 6 months, then a 6-month continuation phase.

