7.1.3.3 Safety set

Safety analysis will include all subjects entered continuation phase and safety data will be presented. Any AE and SAE occurring after the date of visit 9 to the date of Visit 13 will be reported as happening in the continuation phase and will be reported according to the randomization arm that the subject was assigned. For comparison of safety in the two periods, the safety set is composed of all subjects in study period and continuation phase and assessed and analyzed as members of each period.

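### Lost days from school or work are summarised per phase without a denominator, although with a split at Visit 9 the control arm's AHCL phase is about 15-18% shorter than its MDI phase

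*SAP*

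**What the plan says.** SAP 7.9.1.3.10 (control group) and 7.9.2.3.10 (treatment group) carry the same single sentence on lost days: "Summary number of lost days from school or work will be reported during study phase and continuation phase". Neither gives an exposure, a rate or dates for the phases.

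SAP 5.1 treats the phases as equal: "followed by a study phase of 6 months, then a 6-month continuation phase". The protocol's visit schedule (9.3) puts the end of the study phase two weeks after the 6-month visit: "Visit 9: End of Study Phase / Pump Start [Visit 8 + 14 days (Window + 7 days)]". In the control arm the pump starts at that visit. SAP 7.1.3.3 assigns adverse events after Visit 9 and up to Visit 13 to the continuation phase, and 7.9.1.3.6 uses the same span for sensor use and calls it 6 months.

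Other event endpoints are adjusted for exposure. Severe hypoglycaemia (7.10.1) and DKA (7.10.2) get rates per 100 patient-years, and biochemical hypoglycaemic events (7.9.1.3.1) are per week of sensor wear. SAEs, SADEs, USADEs and device deficiencies (7.10.3) are plain numbers, and the sentence names the run-in and study phases, not the continuation phase. Yet 7.1.3.3 foresees a comparison between periods: "For comparison of safety in the two periods, the safety set is composed of all subjects in study period and continuation phase".

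**The concern.** SAP section 7 says that the analysis centres on the control group's outcomes in the study period against the continuation phase. For that group this contrast is MDI against AHCL. A count accumulates with time, so if the AHCL phase is shorter, a count or per-subject mean is lower there even when the underlying rate has not moved. The distortion runs in one direction, towards the device, and a reader told that both phases last 6 months could not see it in the table.

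**Working it through.** **Inputs (target intervals, Protocol 9.3 and 9.4; month = 30.44 days)**
- Randomisation (Visit 4) to Visit 5, control arm: "Visit 5: Follow-up call [Visit 4 + 7 days", so 7 days.
- Visit 5 to 7A: "Visit 7A [Visit 5 + 3 months". Treatment arm: the same interval from Visit 5A.
- Visit 7A to 8: "Visit 8: Follow-Up Visit [Visit 7A + 3 months".
- Visit 8 to 9: 14 days.
- Control arm after Visit 9: 7 days to 11A, 7 days to 11C, 1 month to 11E, 1 month to Visit 12 ("Visit 12 [Visit 11E + 1 month (Window ± 10 days)]"), 3 months to Visit 13.
- Treatment arm: Visits 10, 11 and 12 at 1-month steps counted from Visit 8, then 3 months to Visit 13.

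**Can the stated 6 + 6 months be reproduced?**
- Split at Visit 8: Visit 5 to 8 = 6 months = 182.6 days. Visit 8 to 13 = 14 + 14 days + 5 months = 180.2 days in controls (5.92 months) and 182.6 days in the treatment arm. This reproduces 6 + 6.
- Split at Visit 9: it does not.

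**Phase lengths with Visit 9 as boundary**
- Study phase from Visit 5/5A: 182.6 + 14 = 196.6 days (6.46 months). From Visit 4: 7 + 182.6 + 14 = 203.6 days (6.69 months).
- Continuation, controls: 14 + 5 × 30.44 = 166.2 days (5.46 months).
- Continuation, treatment arm: 182.6 − 14 = 168.6 days (5.54 months).

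**Shortfall at a constant rate**
- Controls: 1 − 166.2/196.6 = 15.5%; 1 − 166.2/203.6 = 18.4%.
- Treatment arm: 1 − 168.6/196.6 = 14.2%; 1 − 168.6/203.6 = 17.2%.
- With 28-day months the control range is 15.4-18.5%; with 30-day months, 15.5-18.4%.
- Illustration, assuming 2 lost days per 6 months throughout: controls expect 2 × 196.6/182.6 = 2.15 to 2.23 days in the study phase and 2 × 166.2/182.6 = 1.82 in the continuation phase. Divided by time, the two phases agree.

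**Same calculation with Visit 8 as boundary**
- Controls: 1 − 180.2/182.6 = 1.3% (from Visit 5) to 1 − 180.2/189.6 = 5.0% (from Visit 4).
- Treatment arm: 0% to 3.7%.

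**Visit windows, control arm, split at Visit 9**
- All windows at minimum: 7 + 6 + 16.4 + 20.4 + 81.3 = 131 days. All at maximum: 14 + 14 + 44.4 + 40.4 + 101.3 = 214 days.
- If visits fall uniformly within their windows (an assumption), the mean continuation phase is 166.2 + 3.5 + 3 = 172.7 days. The mean study phase is 196.6 + 3.5 = 200.1 or 203.6 + 3.5 = 207.1 days. The gap is 14-17%, and in simulation about 1-3% of subjects have a continuation phase at least as long as their study phase.

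**Serious events and device deficiencies, only if raw counts are compared between periods**
- Planned numbers per arm: 70/2 = 35 randomised and 64/2 = 32 completing. Assumption: the 3 dropouts contribute half the phase each.
- Control person-time, study phase: (32 + 1.5) × 196.6/365.25 = 18.0 years, or 18.7 years from Visit 4. Continuation: 32 × 166.2/365.25 = 14.6 years.
- Fall in expected counts at unchanged risk: 19-22%.

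**The case against.** Five points can be made against this.

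- **The boundary is not stated for lost days.** HbA1c, weight and the questionnaires use Visit 8 as the 6-month point, and a Visit 8 split nearly removes the gap. This stands, so the 15-18% is conditional. Visit 9 is still the more natural reading: it is the SAP's stated split for adverse events and sensor use, and controls remain on MDI until then, so a Visit 8 split would put about two weeks of MDI into the AHCL phase.
- **The summary need not be a raw total.** SAP 7.2 describes continuous variables by n, mean, median and spread, so a per-subject mean is a fair reading. That does not help, because the mean falls by the same percentage.
- **Dropouts are already handled for lost days.** This stands. SAP 7.1.3.1 restricts ancillary endpoints to subjects who entered the continuation phase, so study-phase dropouts contribute to neither phase. Only exits during the continuation phase add to the shortfall.
- **Safety counts.** A reader might infer that the SAP plans a table in which serious events fall by 19-22% on AHCL. The documents do not support that: 7.10.3 names only run-in and study phase, and the between-period comparison appears only in 7.1.3.3. The figure is what would follow if that comparison used raw counts.
- **The windows.** A reader might take 131 days as the likely continuation phase. It is one extreme; the same windows allow about 214 days, longer than the target study phase.

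Tables 5 and 6 list no procedure that collects lost days, and the case report form is under separate cover, so the recall period cannot be checked.

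**Conclusion.** The point holds for lost days in the control arm. If Visit 9 divides the phases and visits follow their target dates, an unadjusted per-phase summary would show about 15-18% fewer lost days on AHCL at an unchanged rate. With Visit 8 as the divider the gap is 0-5% across both arms.

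It does not hold for event counts in general, since severe hypoglycaemia, DKA and biochemical hypoglycaemia have exposure-adjusted rates. For SAEs, SADEs, USADEs and device deficiencies it is conditional on a between-period comparison of raw counts, where study-phase dropouts would add to the effect. In the treatment arm both phases are AHCL, so the 14-17% there is not a therapy contrast.

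The consequence is small. All analyses in this SAP are exploratory, lost days is an ancillary endpoint with only a summary specified, and no primary, secondary or hierarchical test is touched. It is more than missing detail, because the summary as described would tilt a descriptive MDI-against-AHCL comparison towards the device.

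**What to change.** - **SAP 7.9.1.3.10 and 7.9.2.3.10:** state the start and end date of each phase, and the recall period to which the recorded lost days refer. Report lost days per patient-year (or per 6 months) of each subject's actual time in the phase, with the counts alongside.
- **SAP 7.10.3:** reconcile the phases named there with the between-period comparison in 7.1.3.3, and add rates per 100 patient-years using the formula in 7.10.1.
- **SAP 7.10.1:** before its formula is reused, reconcile its two starting points for the continuation phase, Visit 9 in one sentence and after Visit 10 in another.

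The cost is a few sentences of SAP wording and one extra column in the tables. The formula already exists, and 7.1.3.3 already relies on the dates of Visits 9 and 13. No new visit or sample size is needed; whether the case report form already supports the split of lost days cannot be confirmed from these documents.

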7.9.1.3.11 Questionnaires' scores

The Hypoglycemia Fear Survey (HFS) score, Diabetes Treatment Satisfaction Questionnaire (status version, DTSQs and change version DTSQc) scores and Diabetes Quality of Life Questionnaire (DQoL) will be calculated in each study arm and reported using descriptive statistics for quantitative variables.

Hypoglycemia Fear Survey (HFS)

Hypoglycemia can lead to various aversive symptomatic, affective, cognitive, physiological, and social consequences, which in turn can lead to the development of possible phobic avoidance behaviors associated with hypoglycemia. The hypoglycemia fear survey (HFS) is a psychometric instrument designed to quantify this fear. The instrument has internal consistency and test-retest stability and varies with elevated glycosylated hemoglobin. The HFS has in most translations two subscales, the behavior subscale and the worry subscale and has a recollection period of 6 months. The two subscales of the HFS are scored as: behavior subscale (first 15 items) items are added together, the 18 Worry subscale items are added together. Additionally, a total score, adding all 33 items, will be computed. Descriptive statistics for the HFS score (behavior, worry and total) will be reported for Visit 2 (baseline), visit 8 (end of 6 months) and visit 13 (end of 12 months).

DTSQs and DTSQc

The Diabetes Treatment Satisfaction Questionnaire (DTSQ) has been specifically designed to measure satisfaction with diabetes treatment regimens in people with diabetes. The DTSQ [status version (DTSQs)] is an eight-item questionnaire, in which six questions (items 1, 4, 5, 6, 7 and 8) assess treatment satisfaction and the other two assess perceived frequency of hyper- and hypoglycemia. Each item is scored from 6 (very satisfied) to 0 (very dissatisfied) such that the Treatment Satisfaction score can range from 36 (very satisfied) to 0 (very dissatisfied) and the perceived frequency of hyper- and hypoglycemia scores range from 6 (most of the time) to 0 (none of the time).

Although the DTSQs has proved highly sensitive to change, in many studies where patients are very satisfied with treatment used at baseline, the DTSQs cannot show improvements when they switch to a new treatment, even though they might be even more satisfied with the new treatment. To overcome the limitation of the DTSQs, a change version (DTSQc) has also been developed, which asks participants to rate how their current treatment compared with their previous treatment.

The DTSQc instrument contains the same 8 items as the DTSQs version. The difference lies in the wording of the response options and instructions, which, in the DTSQc, direct the respondent to compare their experience of treatment before the study began. All items are rated from +3 to -3. The DTSQc instructions and response options differ from those of the DTSQs to produce measures of relative change in satisfaction rather than measures of absolute satisfaction:

Treatment satisfaction (change): items 1, 4, 5, 6, 7 and 8 are summed to produce a Treatment Satisfaction (change) score (range: +18 to -18). The higher the score, the greater the improvement in

satisfaction with treatment; the lower the score, the greater the deterioration in satisfaction with treatment. A score of 0 represents no change.

A major advantage of the DTSQs and DTSQc is that they have been developed to be suitable for people with type 1 or type 2 diabetes using a wide range of treatments, including various methods of insulin delivery, oral medications and diet alone, and is, therefore, appropriate for use before and after patients switch between very different treatment regimens.

Descriptive statistics for DTSQs will be reported for Visit 2 (baseline), visit 8 (end of 6 months) and visit 13 (end of 12 months).

Diabetes Quality of Life Questionnaire (DQoL)

DQoL has been widely used to measure quality of life among diabetes patients. The instrument has four scales: satisfaction with treatment, impact of treatment, worries about future effects of diabetes, and worries about social and vocational issues. The instrument also includes a generic health item that does not contribute to the scales. A score will be obtained for each dimension. A higher score represents higher quality of life. Descriptive statistics for the DQoL score will be reported for Visit 2 (baseline), visit 8 (end of 6 months) and visit 13 (end of 12 months).

7.9.2 Exploratory Analysis for Treatment group

7.9.2.1 Primary Endpoint: Mean HbA1c

As the treatment group were still using AHCL therapy during the continuation phase, the goal is to check the equivalence of the mean HbA1c from the end of study phase (6 month) to the end of continuation phase (12 month) within control group (MDI+FGM). The within group difference in the mean HbA1c will be compared using the following hypotheses:

Null-hypothesis: $H_0: HbA1c_{\text{continuation phase}} \geq HbA1c_{\text{study period}} + 0.3\%$

Alternative hypothesis: $H_a: HbA1c_{\text{continuation phase}} < HbA1c_{\text{study period}} + 0.3\%$

Where $HbA1c_{\text{study period}}$ is the mean HbA1c (6 months [Visit 8]) of the control group, and $HbA1c_{\text{continuation phase}}$ is the mean HbA1c (12 months [Visit 13]) of the control group. The null hypothesis will be tested against the alternative hypothesis using paired t test if normality assumption is met, Wilcoxon signed rank test if normality assumption is rejected.

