4.1.2 Objective for Treatment Group

The primary objective is to confirm the long-term benefits of AHCL therapy. The non-inferiority on glycemic control of the AHCL system in continuation phase versus in study period will be tested.

5. Investigation Plan

This study is a pre-market, multi-center, prospective, open label, adaptative, confirmatory, randomized controlled trial in insulin-requiring adult subjects with type 1 diabetes on MDI therapy. The study period for each subject will be approximately 13 months.

Figure 1: Study Design

The study consists of two separate cohorts, Cohort A with subjects on MDI + FGM (confirmatory part of the study) and Cohort B with Subjects on MDI + Real-Time CGM (exploratory part of the study). Each cohort will have a separate randomization.

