7.2 General Methodology

The data from control group and treatment group will be evaluated independently for all endpoints. Also, Cohort A and Cohort B will be analysed independently.

Summary statistics for Continuous variables will be represented by number of subjects(n), mean, median, standard deviation, minimum and maximum and categorical variables will be represented by counts and percentages. P-values for hypothesis testing will be evaluated based on two-sided testing using significance level of 0.05. Confidence intervals will be reported as two-sided 95% confidence intervals. For comparison of primary, secondary, and ancillary endpoints, normality will be verified for appropriate statistical methodology. Comparisons between the study phase and the continuation phase will be performed using a paired T-test for testing the statistical significance of the difference in continuous variables if normality assumption is met or Wilcoxon signed rank test in continuous variables if normality assumption is not met.

The templates for Tables, Listings and Figures (TLFs) will be available in the TLFs document.

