7.5.2 Exploratory Analysis for Treatment Group

The following hierarchical test procedure reflects the relative importance of the endpoints and controls for multiplicity.

Fixed sequential testing of primary and selected secondary endpoints

For the following endpoints, the procedure test hierarchically the ordered hypotheses in sequence at level $\alpha=0.05$ until a first hypothesis is non-rejected.

Primary endpoint

1. Change in HbA1c

Change in HbA1c will be tested using a non-inferiority test with margin of 0.3%, as described in section 7.9.1 and a p-value < 0.05 will be considered statistically significant. If p-value < 0.05 , continue to next test, else stop.

Secondary endpoints

2. Percentage of time spent in hyperglycemic range with SG > 250 mg/dL

Non-inferiority test with non-inferiority margin of 6%, if p-value < 0.05 reject null hypothesis and continue, else stop

3. Percentage of time spent in hyperglycemic range with SG > 180 mg/dL

Non-inferiority test with non-inferiority margin of 6%, if p-value < 0.05 reject null hypothesis and continue, else stop

4. Percentage of time spent within range 70 - 180 mg/dL

Non-inferiority test with non-inferiority margin of 6%, if p-value < 0.05 reject null hypothesis and continue, else stop

5. Percentage of time spent in hypoglycemic range with SG < 54 mg/dL

Non-inferiority test with non-inferiority margin of 2 %, if p-value < 0.05 reject null hypothesis and continue, else stop

6. Percentage of time spent in hypoglycemic range with SG < 70 mg/dL

Non-inferiority test with non-inferiority margin of 5 %, if p-value < 0.05 reject null hypothesis and continue, else stop

Additional analysis

Analyses on ancillary endpoints and safety endpoints may be performed, and p-values will be reported but may not be claimed.

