7.9 Evaluation of Objectives

7.9.1 Exploratory Analysis for Control group

7.9.1.1 Primary Endpoints: Mean HbA1c

As the control group switched to AHCL therapy during the continuation phase, the goal is to compare the mean HbA1c from the end of study phase (6 months) to the end of continuation phase (12 months) within control group (MDI+FGM). The within group difference in the mean HbA1c is of primary interest and will be compared using the following hypotheses:

Null-hypothesis: $H_0: HbA1c_{\text{study period}} = HbA1c_{\text{continuation phase}}$

Alternative hypothesis: $H_a: HbA1c_{\text{study period}} \neq HbA1c_{\text{continuation phase}}$

Where $HbA1c_{\text{study period}}$ is the mean HbA1c (6 months [Visit 8]) of the control group, and $HbA1c_{\text{continuation phase}}$ is the mean HbA1c (12 months [Visit 13]) of the control group. The null hypothesis will be tested against the alternative hypothesis using paired t test if normality assumption is met, Wilcoxon signed rank test if normality assumption is rejected. Superiority of AHCL will be concluded if $HbA1c_{\text{study period}} > HbA1c_{\text{continuation phase}}$.

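### SAP 7.9.2.1 defines the treatment group's month 6 to month 12 HbA1c non-inferiority test on the control arm, so as written it does not test whether the AHCL benefit lasts

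*SAP*

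**What the plan says.** The objective for the treatment group (SAP 4.1.2) is durability: "The non-inferiority on glycemic control of the AHCL system in continuation phase versus in study period will be tested".

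Section 7.9.2.1 sits under the treatment-group heading and starts on the right arm: "As the treatment group were still using AHCL therapy during the continuation phase, the goal is to check the equivalence of the mean HbA1c". The same sentence then continues "from the end of study phase (6 month) to the end of continuation phase (12 month) within control group (MDI+FGM". The null hypothesis is that the continuation-phase mean is at least 0.3% above the study-period mean, and the alternative is that it is less than 0.3% above. The study-period term "is the mean HbA1c (6 months [Visit 8]) of the control group", and the continuation-phase term "is the mean HbA1c (12 months [Visit 13]) of the control group".

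The treatment-group testing sequence (SAP 7.5.2) has this HbA1c test as step 1, specified as a "non-inferiority test with margin of 0.3%, as described in section 7.9.1". Section 7.9.1 is the control-group section. Its HbA1c test (7.9.1.1) is a two-sided test of a difference, read as superiority, and it opens: "As the control group switched to AHCL therapy during the continuation phase".

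Section 7.2 adds: "The data from control group and treatment group will be evaluated independently for all endpoints".

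**The concern.** The heading and the objective point to one arm, while every operative term points to the other. The comparison group and both parameters of the hypotheses are the control group's, and the cross-reference in 7.5.2 leads to the control-group section. No sentence in the SAP defines the HbA1c hypothesis on treatment-arm means.

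The arms differ in what happened to them. The treatment arm is on AHCL at both visits, so its change from Visit 8 to Visit 13 measures durability. The control arm is on MDI at Visit 8 and on AHCL at Visit 13, so its change measures the effect of switching.

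The test is step 1 of a fixed sequence that stops at the first failure, and section 7.12 commits to carrying out the whole SAP. Run literally, a switch effect in the other arm would open the five treatment-group CGM tests and could be reported as maintained benefit.

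**Working it through.** **1. The passages side by side**

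| Place in SAP | Arm named | Type of test |
|---|---|---|
| 4.1.2 objective | Treatment | Non-inferiority, AHCL continuation phase vs AHCL study period |
| 7.9.2 heading and opening clause of 7.9.2.1 | Treatment | Called equivalence |
| 7.9.2.1 goal sentence, remainder | Control (MDI+FGM) | – |
| 7.9.2.1 both hypothesis terms | Control | One-sided non-inferiority, margin 0.3% |
| 7.5.2 step 1 | Treatment (by heading) | Non-inferiority, margin 0.3%, referred to 7.9.1 |
| 7.9.1.1 | Control | Two-sided difference, superiority, no margin |

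For contrast, step 1 of the control-group sequence (7.5.1) cites 7.9.1.1 correctly. Protocol 9.1 confirms that the control arm crosses over to AHCL after the 6-month study phase.

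**2. What the written test adds (no assumptions about effect size or SD)**

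Let D = HbA1c at Visit 13 minus HbA1c at Visit 8 in the control arm, and let U be the upper limit of the two-sided 95% interval for mean D.

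- Superiority in 7.9.1.1 is shown when U < 0.
- The test written in 7.9.2.1 passes when U < 0.3.

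Since 0 < 0.3, the first implies the second. Subtracting a constant does not alter normality, so the same branch (paired t or Wilcoxon signed rank) applies to both tests, and the implication holds in either. If the non-inferiority p-value were read as one-sided 0.05, the limit would be lower still and the implication would hold as well. The written step 1 therefore adds nothing about durability once 7.9.1.1 succeeds.

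**3. Illustration of the size**

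SAP section 6 states that no power analysis was done for this phase, so there is no plan figure to reproduce for this test. I borrow n = 32 per arm, SD 0.7 and effect 0.5 from the between-arm sizing in SAP 6.2. That sizing does reproduce: a two-sample t-test gives 31.76, hence 32 per arm, with power 0.803. Using these values for a paired 6-to-12-month change is my assumption. I therefore vary the SD, including the 0.83 that 6.2 also quotes.

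The paired test passes when (mean D − 0.3)/(SD/√n) < −t(0.975, 31) = −2.04. The noncentrality is (δ − 0.3)/(SD/√32), where δ is the true mean change. For δ = −0.5 and SD 0.7 it is −0.8/0.1237 = −6.46.

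| True control-arm change δ | SD 0.7 | SD 0.83 | SD 1.0 |
|---|---|---|---|
| −0.5 | above 0.999 | above 0.999 | 0.992 |
| −0.25 | 0.990 | 0.95 | 0.854 |

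These are the probabilities that the written test passes, whatever happens in the treatment arm. If the treatment arm truly lost the full 0.3, the intended test on that arm would have noncentrality 0 and would pass 2.5% of the time at any SD.

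**The case against.** The strongest reply is that this is a copying slip from 7.9.1.1 and that the intended analysis is clear. The heading, the opening clause, objective 4.1.2 and the rule in 7.2 that the groups are evaluated independently all point to the treatment arm. Section 7 also announces a similar analysis for the treatment group. Section 8 requires independent programming of the primary endpoint, which gives a second reader the chance to notice. Section 7.12 allows deviations with justification. Everything in this SAP is exploratory, and the pass probabilities rest on borrowed inputs.

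Most of this stands. The intent can be recovered, carried-over text is the likely cause, a literal run is not the most probable outcome, and the confirmatory comparison is not affected. The wording error needs no probability calculation to establish it.

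It does not remove the error. A SAP exists to fix the tested quantity before the data are seen, and here the definitions and the cross-reference both name the wrong arm. An independent programmer who works from the definitions would reproduce the mistake. A programmer who works from the intent would be departing from the written SAP, which 7.12 then requires to be described and justified. The exploratory label also sits beside an objective of confirming long-term benefit and a sequence said to control multiplicity, so the report is likely to lean on this test.

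**Conclusion.** The concern holds. As written, step 1 of the treatment-group sequence is a non-inferiority test of AHCL against MDI within the control arm, not a test of whether the AHCL benefit is kept. It passes automatically whenever control-group superiority is shown in 7.9.1.1. That conclusion needs no assumption about effect size or SD. Under the borrowed inputs (32 pairs, SD 0.7 to 1.0, control-arm fall of 0.5) it passes with probability of at least 0.99 regardless of the treatment arm, whereas the intended test would pass 2.5% of the time if that arm had truly lost 0.3.

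The wording of equivalence is a second, smaller mismatch, because the hypotheses are one-sided.

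This should be corrected before the analysis is run. The stake is the long-term benefit statement in the final report, within an exploratory phase. The randomised primary comparison is unaffected. Confidence in the wording error is high.

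**What to change.** In SAP 7.9.2.1:

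- In the goal sentence, name the treatment group (AHCL) in place of the control group (MDI+FGM). This also removes a label that cannot fit Cohort B, to which section 7 applies as well.
- Define both the Visit 8 and the Visit 13 HbA1c means on the treatment group.
- Replace the word equivalence by non-inferiority.

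In SAP 7.5.2, step 1, change the cross-reference from 7.9.1 to 7.9.2.1.

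While the text is open, check 7.9.2.3.1 for the same carry-over: it sits in the treatment-group section but sets its margin from the control group's observed mean.

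The cost is a few words and one section number in the SAP. No new data, analysis or change of design is needed.
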